## THE CLINICAL NEED

Despite the use of both the Perclose™ and the Angio-Seal™ commonly for TFA closure there has been no clinically established time to ambulation post-deployment. While time to ambulation varies widely based on operator in both diagnostic and PCI catheterizations (which require anticoagulation), the Perclose™ instructions for use indicate that a patient may ambulate 2 hours after their device is deployed if using a 5-8F sheath and similarly Angio-seal™ recommends ambulation 2 hours after deployment. Particularly for Perclose™, which could otherwise be considered ideal over Angio-Seal™ given its properties allowing for immediate re-access, reducing time to hemostasis and ambulation would be important. To this end, the utility of PFHP would be of particular interest in those undergoing TFA with a Perclose™. While the PFHP have been shown to be safe and decreased time to hemostasis when used in conjunction to manual compression, it has not been studied in conjunction with a closure device. PFHP in conjunction with manual pressure is most commonly used in the catheterization lab when a contraindication to a closure device exists such as severe arterial disease, but may also improve time to hemostasis and ambulation when used in conjunction with a Perclose™. Establishing a safe expedited protocol with use of a closure device and a PFHP could result in multiple favorable clinical and hospital outcomes:

- Decreased femoral artery hemostasis times
- Decreased incidence of oozing, bleeding or hematoma complications
- Facilitate arterial site management to the more specialized catheterization lab staff/personnel that are better trained to recognize complications
- Decreasing time in the cath lab trying to obtain hemostasis, therefore increasing case throughput and number of cases per day
- Decreasing the workload to the staff by virtue of shortened band in place times and improve procedural throughput.
- Facilitate greater patient comfort resulting from decrease supine time and faster wound healing
- Facilitated faster discharge time allowing for more beds to be available during time of critical bed shortages.

Through our pilot study of 180 patients and multicenter randomized clinical trial of 443 TRA patients we were able to show the capabilities of an adjunct PFHP to an additional standard of

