care closure device to achieve many of those favorable clinical outcomes. We showed time to complete TRB deflation was  $66 \pm 14$  min with the PFHP vs.  $113 \pm 56$  min for TRB alone ( $P < 0.001$ ) in the setting of no minor rebleeding in the TRB + PFHP group. Furthermore, among PCI patients, time to TRB deflation ( $68 \pm 15$  vs  $138 \pm 62$  min,  $P < 0.001$ ) and composite complications [10.0% vs. 24.2%,  $p=0.04$ ] were reduced with the PFHP.

Thus, the Statseal was demonstrated to facilitate a rapid deflation protocol with the TRB, allowing for an earlier discharge, without evidence of significantly increased complication of hematomas or radial artery occlusion. The present study is designed to evaluate the use of Statseal in the TFA population in conjunction with use of the Perclose™ TFA closure device.

Additionally, the TFA is the preferred approach for transcatheter aortic valve replacement (TAVR). In contrast to the 6Fr TFA, TAVR procedures require large bore catheters of 14 to 16 Fr in many circumstances. There has been widespread adoption of the Perclose™ TFA closure device, with many institutions, including our own using a single Perclose closure in order to hemostasis. The present study is designed to evaluate the use of Statseal in the TAVR TFA population in conjunction with use of a single Perclose™ TFA closure device.

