### **III. STUDY OBJECTIVE(S)**

The primary objectives of this study are to evaluate the performance of StatSeal Advanced used in conjunction with the Perclose™ (SS) as compared to the Perclose™ without SS (PC) relative to:

TAVR Outcomes:

1. Primary outcome: Time to Hemostasis (TTH)
2. Secondary outcome: The incidence of access hematomas

Time to hemostasis (TTH) is defined as the time period required to achieve hemostasis, beginning at the time at which the Perclose™ is deployed to the access site to when no additional bleeding is appreciated..

Hematoma are defined as being <5 cm, 5-10 cm, and >10 cm. The physician on the study team will make the assessment for the incidence and size of the hematoma based on physical exam and /or diagnostic imaging including ultrasound. Hematoma assessment will be done in multiple incidences: at the time of Perclose deployment while in the catheterization lab, at the time of admission to the recovery unit by the TAVR team, and at the time of admission to the inpatient service for overnight monitoring. While in recovery the patient will be evaluated by the staff for 15 minutes for one hour, every 30 minutes for the next hour, and every hour for the subsequent four hours (for a total of 6 hours post-procedure while in the recovery unit). While admitted for overnight monitoring (at least for a 24 hour period), the patient will have their site evaluated every 4 hours until the 24 hours period has been reached.

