### **IV. STUDY DESIGN AND METHODOLOGY**

#### **STUDY DESIGN**

This study is a physician initiated, prospective, observational, two arm, randomized study to be performed at one academically affiliated with high catheterization volumes. Enrollment will continue at each site on discretion of the investigators until at least 50 patients are enrolled. Clinicians will perform the catheterization in accordance with local standard practice, with no minimum amount of anticoagulation required during the procedure.

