Randomization will be performed by means of sealed envelopes in randomization blocks of 25. Each envelope will be labeled by patient number containing device designation. Device designation in the envelopes will be random in occurrence. When a patient is officially enrolled (after Perclose™ deployment) the envelope corresponding to that patient number in the Study Patient log will be pulled, opened, and the assignment revealed.

End of Study Status / Effect of Withdrawals:

A subject will have completed the study when one of the following events is documented:

1. The patient is successfully enrolled, treated with a Perclose™, and completes all required follow up.

2. A subject withdraws consent to participate. Patients who withdraw from the study will have their data included to the extent allowable by law. As all study related procedures are expected to be completed on the day of the procedure or day after, subject withdrawal is not considered likely.

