### **VI. STUDY STATISTICAL PLAN:**

This is a physician initiated, prospective, randomized, two-arm study, to be conducted at high-

volume academically affiliated centers with the cath lab staff having a (minimum) ten case experience using StatSeal Advanced. The primary analysis will be by intention-to-treat methodology.

A sample size of 50 patients is sufficient to have >90% power to detect an average expected difference of 10 minutes in time (5 min vs 15 min) to hemostasis (different primary outcomes compared to 6F study) between the SS and Perclose groups, using a two-sided alpha of 0.05. A standard deviation of 10 minutes is assumed, which will be the additional time for manual compression if any site oozing/bleeding is seen after the initial compression. A different standard deviation time was assumed given larger bore access for TAVR TFA access.

Descriptive summary statistics will be presented for all study variables. Continuous variables will be displayed as means with standard deviations and medians with 75th and 25th percentiles. Categorical variables will be summarized as frequencies with their respective percentages with two-sided 95% exact confidence intervals of the percentages. Statistical comparisons for continuous variables will be performed using the Student's t test or Mann-Whitney U test, as appropriate. Comparisons for categorical variables will be performed using the Chi square test or Fisher exact test, as appropriate. A two-sided P value of 0.05 will be considered statistically significant.

A single multivariate logistic regression will be reported for the safety outcome of hematoma formation. In order to create this model, study arm and variables known to place patients at higher risk for hematoma formation will be tested in univariate analysis for the primary safety outcome. Those variables with a P<0.10 will be included in backwards stepwise regression modeling to obtain a final model. Similar to our prior published study, the following variables will be analyzed: Age, sex, weight, hypertension, diabetes, creatinine, pre-procedural INR, pre-procedural platelet level, heparin dose given, PCI, last ACT prior to procedural end, and last SBP prior to procedural end.

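### Hematoma is compared between arms only through tests for a difference, with no confidence interval for that difference, so a non-significant P value alone cannot support a safety statement

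*Combined protocol and SAP*

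**What the plan says.** Section V names hematoma, in three size classes, as the primary safety outcome. Section III ranks it lower ("Secondary outcome: The incidence of access hematomas"). That conflict needs settling but is separate from this point.

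Section VI treats hematoma in three ways:

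- **Test.** Categorical outcomes are compared by Chi square or Fisher exact test, whichever is appropriate, and "A two-sided P value of 0.05 will be considered statistically significant".
- **Description.** Categorical variables are given as frequencies and "percentages with two-sided 95% exact confidence intervals of the percentages". These are intervals for percentages. Nothing in the section specifies an interval for the difference between arms.
- **Model.** One multivariable logistic regression is planned for hematoma. Study arm is one of the candidates. Candidates with univariate P<0.10 go into backward stepwise selection, with no stated threshold for staying in.

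The only sample-size reasoning is for time to hemostasis: "A sample size of 50 patients is sufficient to have >90% power to detect an average expected difference of 10 minutes in time". No expected hematoma rate, acceptable excess, margin or power for hematoma is given.

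**The concern.** The rationale in Section I looks for speed together with safety: "Establishing a safe expedited protocol with use of a closure device and a PFHP could result in multiple favorable clinical and hospital outcomes". Faster hemostasis is worth having only if hematomas do not rise, so the reader of the results will want to know how large an excess the data rule out. A test for a difference does not answer that. In a small trial it is usually non-significant whether or not harm is present.

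The logistic model does not fill the gap. It also looks for a difference, and if study arm fails the screen or the stepwise selection, the final model contains no treatment effect for the safety outcome.

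The likely misreading has a precedent in the document. Section I sums up the earlier radial-access work as "without evidence of significantly increased complication of hematomas or radial artery occlusion". That work had 180 and 443 patients. The same sentence written from about 50 patients would carry much less weight.

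**Working it through.** **Inputs.** Total 50 patients, two-sided alpha 0.05, SD 10 min and difference 10 min (Section VI). Twenty-five per arm is an assumption: enrollment runs "until at least 50 patients are enrolled", so 50 is a minimum. No allocation ratio is stated, and "Randomization will be performed by means of sealed envelopes in randomization blocks of 25" cannot give an exact 1:1 split within a block. Hematoma is taken as yes/no, as the logistic model implies. Control rates are assumptions, because the documents give none.

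**1. The plan's own figure.** Noncentrality = 10 / (10 × √(2/25)) = 3.536. Normal approximation: Φ(3.536 − 1.960) = 94.2%. Noncentral t with 48 df: 93.4%. The claim of more than 90% power for time to hemostasis is reproduced. It says nothing about hematoma.

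**2. Smallest observed excess with P<0.05.** All 25 v 25 tables were enumerated. Each patient is 1/25 = 4 points.

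| Control events | SS events needed, Fisher | Excess (P) | SS events needed, uncorrected chi-square | Excess |
|---|---|---|---|---|
| 0 | 6 | 24 (0.022) | 4 | 16 |
| 1 | 7 | 24 (0.049) | 6 | 20 |
| 2 | 9 | 28 (0.037) | 8 | 24 |
| 3 | 11 | 32 (0.026) | 9 | 24 |
| 4 | 12 | 32 (0.032) | 11 | 28 |
| 5 | 13 | 32 (0.038) | 12 | 28 |

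From 5 to 12 control events the excess stays at 32 (Fisher) and 28 (chi-square). The 16- and 20-point entries have expected counts below 5, where Fisher would normally be chosen. Splits from 24/26 to 20/30, with 0 to 5 control events, give about 21 to 32 points with Fisher.

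**3. Chance of missing a true doubling.** Power is the sum of Bin(a; 25, p₀) × Bin(b; 25, p₁) over all tables with P<0.05.

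| Assumed true rates | Missed, Fisher | Missed, uncorrected chi-square |
|---|---|---|
| 10% v 20% | 1 − 0.086 = 91% | 1 − 0.174 = 83% |
| 20% v 40% | 1 − 0.231 = 77% | 1 − 0.352 = 65% |

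Step 2 gives observed excesses. The true excess that Fisher would detect with 80% power is larger: 34 points from a 5% control rate and 39 from 10%.

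**4. Screen for the logistic model.** For study arm to reach univariate P<0.10, the observed excess must be about 8 to 24 points by likelihood ratio (0 to 7 control events) or 20 to 24 by Wald (1 to 7 control events).

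**5. What an interval would show.** The Newcombe limits for a difference d = p₁ − p₀, with Wilson limits (l, u) for each arm, are:

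- lower: d − √[(p₁ − l₁)² + (u₀ − p₀)²]
- upper: d + √[(u₁ − p₁)² + (p₀ − l₀)²]

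For SS 6/25 and control 3/25, the Wilson limits are 0.115 to 0.434 and 0.042 to 0.300.

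- Lower: 0.12 − √(0.125² + 0.180²) = −0.099
- Upper: 0.12 + √(0.194² + 0.078²) = +0.329

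| SS v control (of 25 each) | Fisher P | 95% upper limit, points |
|---|---|---|
| 0 v 0 | 1.0 | +13.3 |
| 3 v 3 | 1.0 | +19.6 |
| 6 v 3 | 0.46 | +32.9 |
| 1 v 3 | 0.61 | +9.4 |
| 0 v 3 | 0.23 | +3.5 |

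All five results are non-significant, yet the excess they leave open runs from 3.5 to 33 points. At 6 v 3, study arm would also fail the screen in step 4, which needs 8 SS events against 3.

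**The case against.** Several objections have force.

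- **A reader might infer that the plan will call a non-significant result safe.** The documents do not say so. The sentence about earlier trials is background on radial access, and Section VI is silent on wording. Section I also lists fewer hematomas as a hoped-for benefit, and a two-sided test fits that aim. The point is therefore a warning about interpretation; the plan does not contradict itself here.
- **A reader might infer that the Chi square or Fisher test is the sole comparison.** It is not, because the logistic model is a second one. It does not repair the gap, for the reason given above.
- **A reader might infer that 25 per arm can never exclude an excess below some fixed figure, such as 15 to 20 points.** That is wrong. The limit depends on the observed counts, as step 5 shows.
- **The chance of missing a doubling depends on the control rate.** Any hematoma counts, including those under 5 cm, so the rate may not be low. Fisher power for a doubling is 36% at 25% v 50%, 51% at 30% v 60% and 65% at 35% v 70%. The 91% and 77% hold only at the assumed 10% and 20%.

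None of this supplies an interval for the difference, and two separate intervals for percentages do not stand in for one.

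**Conclusion.** The point holds as a gap in analysis and reporting. Both planned comparisons of hematoma look for a difference, the second may drop study arm, and neither is tied to an interval for the between-arm difference. A non-significant P value alone would not support a statement about safety.

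The size is as calculated above. The thresholds rest on 25 per arm and a yes/no outcome, and the miss rates also on the assumed control rates. The 24 to 32 point range belongs to Fisher; the chi-square range is lower and is quoted beside it. The finding does not show that the trial is too small for its efficacy aim, nor that the disc raises hematoma risk. It should be corrected before analysis and does not threaten the primary efficacy result.

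**What to change.** In Section VI:

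1. Make the main hematoma result the SS-minus-control risk difference with a 95% confidence interval (Newcombe or Miettinen-Nurminen), by intention to treat.
2. Report it whether or not study arm survives the logistic model selection.
3. Keep the Chi square or Fisher P value as supporting information.
4. State that non-significance will not be reported as absence of excess risk, and that the safety conclusion will quote the observed upper confidence limit. Write no fixed excludable excess in advance.

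The cost is a few sentences of SAP text and one extra line of output, with no change to sample size, conduct or patient care. The downside is that the safety conclusion will look less favourable than a bare non-significant P value.

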#### Primary Safety Outcome:

- Hematoma formation: small ranging from small <5cm [I], 5-10cm [II] , or large >10cm. Hematoma assessment will be done in multiple incidences: at the time of Perclose deployment while in the catheterization lab, at the time of admission to the recovery unit by the TAVR team, and at the time of admission to the inpatient service for overnight monitoring. While in recovery the patient will be evaluated by the staff for 15 minutes for one hour, every 30 minutes for the next hour, and every hour for the subsequent four hours (for a total of 6 hours post-procedure while in the recovery unit). While admitted for overnight monitoring (at least for a 24 hour period), the patient will have their site evaluated every 4 hours until the 24 hours period has been reached.

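### Study arm is itself put through the P<0.10 screen and backward selection in the only hematoma model, so an adjusted arm effect appears only when its own P value is small

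*Combined protocol and SAP*

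**What the plan says.** All the relevant analysis text is in Section VI (Study Statistical Plan) of the combined protocol and SAP.

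- One adjusted model is planned: "A single multivariate logistic regression will be reported for the safety outcome of hematoma formation".
- Its candidates include the randomized comparison: "study arm and variables known to place patients at higher risk for hematoma formation will be tested in univariate analysis".
- The selection rule follows: "Those variables with a P<0.10 will be included in backwards stepwise regression modeling to obtain a final model". Twelve covariates are then listed. No stay level for the backward step is given, and no variable is exempt from selection.
- Separately, "Comparisons for categorical variables will be performed using the Chi square test or Fisher exact test, as appropriate", and percentages are to be shown "with two-sided 95% exact confidence intervals of the percentages". These are intervals for proportions, not for a difference between arms.

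Section III lists hematoma among the objectives ("Secondary outcome: The incidence of access hematomas"). Section V makes it the primary safety outcome, in an entry that begins "Hematoma formation: small ranging from small <5cm" and continues with two larger size grades.

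**The concern.** Study arm is the randomized contrast, not a candidate predictor. Selecting it on its own P value has two consequences. When the observed arm difference is modest, arm is dropped and the reported model says nothing about the patch, which a reader may take as evidence of no effect on hematoma. When arm survives, it does so because the observed difference was large, so the reported effect is on average larger than the true one. This applies to benefit and harm alike.

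At stake is the estimate for the primary safety outcome. A moderate increase in hematoma would usually leave no trace in the only adjusted model. The other planned output is a P value and separate percentages, neither of which states how much harm the data still allow.

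**Working it through.** **The plan's own figure.** Section VI gives no hematoma rate or hematoma power. Its one power statement (above 90% for time to hemostasis; 50 patients, difference 10 min, SD 10 min, two-sided 0.05) reproduces at 25 per arm: 10/(10·√(2/25)) = 3.54; 3.54 − 1.96 = 1.58; power 94.2% (93.4% with the t distribution). The present point does not depend on it.

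**Inputs.** From Section VI: P<0.10 screen, arm among the screened variables, 50 patients. Assumed: hematoma counted yes/no, 1:1 allocation (no ratio is stated), and the rates below. The screening test is not named, so three are used: Fisher (F); chi-square, switching to Fisher if an expected count is below 5 (C/F; the cutoff is an assumption); and likelihood ratio (LR).

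**Formulas.** With a events of 25 on control (rate p_C) and b of 25 on patch (rate p_S), and weights w(a,b) = Bin(a; 25, p_C) × Bin(b; 25, p_S):

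- P(arm passes) = Σ w(a,b) over all tables with P<0.10.
- Mean observed difference given a pass = Σ w(a,b)·(a−b)/25 over those tables, divided by P(arm passes).

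**Results of exact enumeration, 25 per arm**

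| Control vs patch | Arm passes: F / C/F / LR | Mean difference if passed: F / C/F / LR | True difference |
|---|---|---|---|
| 20% vs 10% | 16.0 / 17.6 / 27.7% | 24.7 / 24.3 / 20.9 points | 10 |
| 30% vs 15% | 25.6 / 32.3 / 36.0% | 29.2 / 27.6 / 26.7 points | 15 |
| 40% vs 20% | 35.2 / 45.8 / 46.4% | 33.2 / 30.9 / 30.7 points | 20 |
| 30% vs 5% | 69.2 / 71.0 / 81.2% | 30.0 / 29.8 / 28.2 points | 25 |

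**Is this only sparse data?** Leaving out trials with a zero-event arm moves the mean differences by at most about 1 point, so the excess comes from selection. On the odds-ratio scale (geometric mean, 0.5 added to each cell, zero-event arms left out), the crude value given a pass at 20% vs 10% is 0.17-0.21. The true value is (0.10/0.90)/(0.20/0.80) = 0.44.

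**Harm.** With control 10% and patch 20%, symmetry gives the same pass rates, so arm is dropped in 100 − 27.7 = 72% to 100 − 16.0 = 84% of trials. When the C/F screen drops it, the mean observed excess is still 7.0 points.

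**Adding the backward step.** A simulation of the full procedure (4,000 trials per setting, C/F or t-test screen, 11 covariates unrelated to hematoma, PCI taken as constant) used stay levels of 0.05 and 0.10. In the harm case arm is in the final model in 14.6% and 16.5% of trials, so it is absent in 84-85%, against 82% from the C/F screen alone.

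**Larger enrolment.** Section IV sets 50 as a minimum. At 50 per arm with the C/F screen, arm passes in 39%, 57% and 72% for the first three rows. The mean differences are then 17, 21 and 24 points against 10, 15 and 20.

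**One table as illustration.** Suppose 5/25 on patch and 2/25 on control. The P value is 0.42 (Fisher) or 0.22 (LR), so arm is dropped. The difference is 20% − 8% = 12 points. The Wilson limits are 8.9-39.1% and 2.2-25.0%, so the Newcombe 95% interval runs from 12 − √(11.1² + 17.0²) ≈ −8 to 12 + √(19.1² + 5.8²) ≈ 32 points. The planned model would omit arm from data that allow a 32-point increase.

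**The case against.** The strongest case is that the randomized safety comparison is already covered. The chi-square or Fisher test is done whatever the screen shows, and in a trial of about 50 an unadjusted comparison is a legitimate main safety analysis. If counts are reported by arm, a reader can derive a risk difference and interval. On this view the logistic model is a risk-factor model modelled on the prior study, and only an adjusted estimate that was never promised is lost. This stands in part: it is why the defect does not invalidate the safety comparison. It does not justify screening the randomized arm, and an interval that a reader could work out is not a planned result.

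The text could also be read as applying the selection rule to the risk variables only, since the list of 12 omits arm. But the sentence before the rule names arm first among the items tested, and nothing exempts it. Even on the other reading, the plan never says that arm stays in.

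Three technical points stand as limits on size.

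- The exaggeration figures are crude, not covariate-adjusted, and at 30% vs 5% the excess is small. There 34-37% of passing trials have a zero-event arm, where ordinary logistic regression has no finite arm estimate whether or not arm is forced in.
- The simulation used covariates unrelated to hematoma, although the plan regards them as risk variables. The conclusion rests on the screen, to which the simulation adds little.
- Much of the silence under harm reflects low power: at 10% vs 20% these tests reach P<0.05 in only 9-18% of trials. A forced-in estimate would be imprecise. But an imprecise estimate shown with its interval is informative, and an omitted one is not.

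**Conclusion.** The concern holds. As written, the only adjusted arm effect on hematoma depends on its own P value. At 25 per arm and assumed rates from 20% vs 10% to 40% vs 20%, arm passes the screen in 16-46% of trials. The mean observed difference when it passes is then roughly 1.5 to 2.5 times the true one (30.7/20 = 1.5; 24.7/10 = 2.5). A doubling of hematoma from 10% to 20% would be dropped at the screen in 72-84% of trials. Larger enrolment reduces the problem without removing it.

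These sizes depend on the assumed rates, 1:1 allocation, a yes/no hematoma outcome and the choice of screening test. The structural fault does not. The unadjusted test remains valid and time to hemostasis is untouched, so this should be corrected but does not undermine the trial.

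**What to change.** Amend Section VI as follows.

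1. Take study arm out of the univariate screen and the stepwise selection, and keep it in any adjusted hematoma model whatever its P value.
2. Replace P-value selection with at most a few pre-randomization covariates, named in advance from the existing list. Last ACT is one candidate: Section IV has it measured before sheath removal, and randomization follows Perclose deployment. The number must be small. At assumed overall rates of 10-30%, 50 patients give 50 × 0.10 = 5 to 50 × 0.30 = 15 events, against 13 candidate terms (arm plus 12). Keeping arm in does not cure that sparsity.
3. Make the between-arm risk difference with a 95% confidence interval (for example Newcombe) the main safety result, beside the planned chi-square or Fisher test. It can be computed even when one arm has no events. State which size grades count as an event.

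The cost is SAP wording only, with no new data, visits or patients. The search for hematoma predictors is lost or becomes a separate analysis labelled exploratory. The interval will be wide: its mean half-width is about 20-23 points at 25 per arm for 20% vs 10% through 40% vs 20%, with coverage of 94.8-96.1%. That width is what a trial of this size can say about hematoma, and the report should show it.

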## **STUDY OVERVIEW GRAPHIC**

### **V. STUDY DEFINITIONS AND OUTCOMES**

#### Definitions of Baseline and Procedural Variables:

Smoking: Active smoking or >20 pack year tobacco history.

Diabetes: Hgb A1C >6.5% or active medical treatment for diabetes.

Hypercholesterolemia: LDL >130 or on treatment with antilipemic agents.

Hypertension: >140/80 or on medical treatment for hypertension.

Diagnostic procedure: Involving diagnostic catheters only.

Interventional procedure: Involving an interventional wire and therapeutic ACT typically >200, including for fractional flow reserve measurement where a stent is not placed.

Puncture attempts: Number of forward advances of the needle (not puncture sites) needed to achieve access

Procedure Start Time: Time when lidocaine is administered, prior to first puncture attempt.

Procedure End Time: Time when sheath is removed

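### The hematoma model screens study arm and 12 covariates and then eliminates backward, with no stated removal rule and probably about one event per candidate or fewer, so its odds ratios and P values lack their nominal meaning

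*Combined protocol and SAP*

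**What the plan says.** Section VI (Study Statistical Plan) commits to reporting a single logistic regression for hematoma formation. Study arm and a list of risk variables are each tested univariately, and then: "Those variables with a P<0.10 will be included in backwards stepwise regression modeling to obtain a final model".

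The list is modelled on the group's earlier radial-access trial: "the following variables will be analyzed: Age, sex, weight, hypertension, diabetes, creatinine, pre-procedural INR, pre-procedural platelet level, heparin dose given, PCI", followed by the last ACT and the last systolic pressure before the procedure ends. That makes 12 covariates, or 13 candidates with study arm.

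The section does not give a removal threshold, a choice between Wald and likelihood-ratio tests, a limit on model size, any penalisation, or an expected hematoma rate. Study arm is screened like the covariates and is not said to be retained. The only general significance level is two-sided 0.05.

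The sample size rests on time to hemostasis alone: "A sample size of 50 patients is sufficient to have >90% power to detect an average expected difference of 10 minutes in time". Hematoma is the secondary outcome in Section III and the primary safety outcome in Section V.

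**The concern.** Selecting variables by their association with the outcome, and then reporting the survivors as though they had been chosen in advance, biases odds ratios away from 1 and makes P values too small and confidence intervals too narrow. The fewer the events per candidate, the worse this is. With very few events a fit can also separate, giving infinite odds ratios.

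This is the only adjusted analysis of hematoma, and the plan commits to reporting it. At stake is a published list of hematoma risk factors for TAVR access that may contain noise and omit real factors. Because the removal rule is unstated, it could also be settled after the data are seen. Making study arm a fixed term would be sensible but would not cure the problem, since the covariates would still be selected.

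**Working it through.** **The plan's own figure.** Inputs from Section VI: 50 patients (25 per arm, taking 1:1), difference 10 min, SD 10 min, two-sided alpha 0.05.

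- Standard error = 10 × √(2/25) = 2.83 min; 10/2.83 = 3.54; 3.54 − 1.96 = 1.58; power = Φ(1.58) ≈ 94.2% (93.4% by noncentral t).
- For 90% power, n per arm = 2 × (1.96 + 1.28)² × (10/10)² ≈ 21.0, taken up to 22.

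The stated power above 90% reproduces. It says nothing about the hematoma model, for which no figure is given.

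**Events per candidate covariate.** Assumed hematoma rates of 10%, 20% and 30% give 5, 10 and 15 events in 50.

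- 5/12 = 0.42; 10/12 = 0.83; 15/12 = 1.25.
- Even 25 events, the most favourable split of 50, give 25/12 = 2.1.

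**Rough check.** For 12 independent exact tests of null covariates, the chance of at least one false positive is 1 − 0.90¹² = 72% at 0.10 and 1 − 0.95¹² = 46% at 0.05. If PCI is effectively constant in TAVR patients, 11 candidates give 69% and 43%.

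**Simulation of the procedure.** Fifty patients, 25 per arm, arm kept in, 12 pure-noise covariates, screen at P<0.10, then backward elimination; 2,000 trials per cell (Monte Carlo error about 1 point). Covariates were all continuous, or 8 continuous and 4 binary, or the latter with moderate correlation. In some Wald runs the screen used t and Fisher tests in place of logistic regression. These covariate distributions are assumptions. The table gives the share of final models keeping at least one noise covariate. The event columns are for 8 continuous and 4 binary covariates with logistic screening.

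| Test, removal threshold | 5 events | 8 | 10 | 15 | Range over all covariate sets |
|---|---|---|---|---|---|
| Wald, 0.10 | 54% | 61% | 61% | 63% | 52–68% |
| Wald, 0.05 | 28% | 36% | 36% | 40% | 28–43% |
| Likelihood ratio, 0.10 | 73% | 74% | 74% | 74% | 70–74% |
| Likelihood ratio, 0.05 | 54% | 55% | 53% | 54% | 52–55% |

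Separate Wald runs that set the hematoma rate at 10%, 20% and 30% agree: 51%, 59% and 60% with removal at 0.10, and 25%, 36% and 39% at 0.05. A repeat at 0.10 gave 48%, 58% and 60%.

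**Further results.**

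- Final model showing a noise covariate at P<0.05 (Wald): about 22–39% of trials.
- A real factor with odds ratio 2 per SD passes the screen in 36%, 55% and 63% of trials at the three rates, so it is lost in 64%, 45% and 37%.
- Separation in the final model: about 11%, 1% and 0%.
- Sensitivity to the event count (Wald): at 25 events, 65% (removal at 0.10) and 42% (0.05); at 3 events, 44–56% and 12–15%. With likelihood-ratio tests at 0.05, 3 events give 55–57%.

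**The case against.** A reader might infer that over half of final models would contain a noise risk factor, or that the trial is more likely than not to report a false independent predictor. The documents do not support either as a general statement. Both need a removal threshold of 0.10, or likelihood-ratio tests at 0.05, and the plan states neither. With Wald tests at the plan's only stated level, 0.05, the share is 25–43%. A covariate retained at P = 0.07 is in the model but is not significant under the plan.

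The figures also assume that all 12 covariates are null, whereas the plan regards them as established risk factors. That stands as a limit on the size. It does not rescue the method, because when factors are real the screen often discards them. The 5 to 15 events are likewise assumed. More events do not help, and the low Wald share at 3 events does not carry over to likelihood-ratio tests. As written, arm is itself screened; the simulation keeps it in to isolate covariate selection.

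A reader might also infer that the plan links 14 versus 16 Fr sheaths to hematoma. It does not. The sentence "A different standard deviation time was assumed given larger bore access for TAVR TFA access" compares TAVR access in general with the 6F study and concerns the SD of time to hemostasis. Leaving sheath size or puncture attempts off the list is a matter of judgement, not an error.

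Finally, Section VI already provides chi-square or Fisher tests for categorical outcomes, so the randomised comparison of hematoma does not depend on this model. That stands and limits the impact.

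**Conclusion.** The concern holds in a limited form. With probably 0.4 to 1.25 events per candidate covariate, screening and backward elimination cannot give a hematoma model whose odds ratios, confidence intervals and P values mean what they say. If all covariates are null and arm is kept, roughly 25–75% of final models retain noise: about 50–68% (Wald) or 70–74% (likelihood ratio) with removal at 0.10, and 25–43% or 52–55% at 0.05. The width of that range is itself a consequence of the missing removal rule.

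These sizes rest on assumed hematoma rates of 10–30%, assumed covariate distributions and 1:1 allocation. They are not a forecast of what this trial will report. The damage is confined to the adjusted model. The change should be made, but the main comparisons do not hinge on it.

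**What to change.** Replace the screening and backward-elimination sentences in Section VI with one pre-specified Firth-penalised logistic model. It should contain study arm, always kept, and at most two covariates known before randomisation and named in advance on clinical grounds, with no data-driven selection.

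Last ACT and one other listed variable would serve. Section IV has ACT measured before sheath removal and randomisation after Perclose deployment, so last ACT precedes assignment. Sheath size could be chosen, but on clinical grounds and not as something the plan ties to hematoma. Show the remaining listed variables descriptively by hematoma status, without claims of independent prediction.

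In simulation the model with arm plus two covariates converged in every trial from 3 to 25 events. Convergence is not precision: 5 events over three coefficients is 5/3 = 1.7 events each, so intervals will be wide.

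The cost is plan wording, with no extra patients; sheath size would need one CRF field if it is chosen and not already collected. The downside is the loss of the exploratory risk-factor model.
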